6.1.1. Leronlimab (PRO 140) - Packaging and Labeling

CONFIDENTIAL Page 56 of 101

Study drug will be packaged, labeled, and shipped by Sherpa Clinical Packaging, LLC.

The contents of each vial are described in Section 6.1. Leronlimab (PRO 140) kits will be labeled with information such as: study protocol #; fill volume; concentration; storage condition; a "use as per study protocol" statement; a cautionary statement; sponsor's name and address; and the kit number.

Below are representative samples of the Investigational Product, finished drug product (FDP) individual vial (Figure 6-1), and kit labels (Figure 6-2) designated for use in this clinical protocol. Each kit contains two labeled vials.

Figure 6-1: Investigational Product - Vial Label

Protocol: CD15_COVID-19 Kit No. xxx	Protocol: CD15_COVID-19 Kit No. xxx
Subject No	Subject No
Single use 3 mL vial contains 2.4 mL of PRO 140 (175 mg/mL) solution for subcutaneous injection	Single use 3 mL vial contains 2.4 mL of PRO 140 (175 mg/mL) solution for subcutaneous injection
Store at 2°C to 8°C (36°F to 46°F)	Store at 2°C to 8°C (36°F to 46°F)
USE AS PER STUDY PROTOCOL	USE AS PER STUDY PROTOCOL
Caution: New Drug – Limited by Federal (or United States) Law to Investigational Use	Caution: New Drug – Limited by Federal (or United States) Law to Investigational Use
CytoDyn Inc., Vancouver, WA, USA	CytoDyn Inc., Vancouver, WA, USA

Figure 6-2: Investigational Product - Kit Label

Protocol: CD15_COVID-19	Kit No. xxx
Site No	Subject No
This kit contains 2 single-use v	rials
Each 3 mL vial contains 2.4 ml	L of PRO 140 (175 mg/mL) solution for subcutaneous injection
Store at 2°C to 8°C (36°F to 46	°F)
USE AS PER STUDY PROTO	OCOL
Caution: New Drug – Limited	by Federal (or United States) Law to Investigational Use
CytoDyn Inc., Vancouver, WA	, USA

The pharmacy manual provides the criteria regarding vial acceptance or rejection, as well as instructions for the preparation of the IP syringes to be used to administer drug.

6.1.2. Leronlimab (PRO 140) - Storage and Handling

Study drug will be shipped at 2°C to 8°C (refrigerated [36°F to 46°F]) to the investigator's site. Upon receipt at the site, the responsible site staff or pharmacist should verify the integrity of the vials. Study drug should be stored at 2°C to 8°C (refrigerated [36°F to 46°F]). The contents of the

CONFIDENTIAL Page 57 of 101

vial should appear as a clear to opalescent, colorless to yellow solution; fine translucent particles may be present. This is normal.

The investigator must maintain an accurate record of the shipment, storage, and dispensing of the study drug in a drug accountability log. An accurate record including the date and amount of study drug dispensed to each subject must be available for inspection at any time. A study CRA assigned to monitor the investigational site will review these documents once study drug has been received by the investigational site. Study drug will be accounted for on an ongoing basis during the study.

6.1.3. Leronlimab (PRO 140) - Administration

Guidelines for dose preparation can be found in the pharmacy manual.

Leronlimab (PRO 140) or placebo will be provided to the administering personnel in single-use syringes prepared from vials of study drug stored at 2-8°C at the site pharmacy prior to use. Syringes will be prepared by an unblinded pharmacist or designated site staff. Each of two syringes is filled to deliver 2 mL of study drug.

Equivalent volumes of PRO 140 will be administered subcutaneously on opposite sides of the abdomen.

A 20-guage needle should be used to remove PRO 140 from vial and a 25-guage needle is used for administration to subjects.

Note: After the leronlimab solution is drawn into the syringe, it can be stored at room temperature (20°C to 25°C, 68°F to 77°F) for up to 2 hours, or refrigerated (2°C to 8°C, 36°F to 46°F) for up to 4 hours.

IP should be administered slowly over 15 seconds per mL.

Following each SC delivery of drug, careful examination will be made to assess the appearance of any study drug Injection Site Reactions (ISRs) as per CTCAE v5.0.

Leronlimab (PRO 140) will be administered as SC injection by a qualified medical professional at the study clinic.

Note: It is preferred that the same injection site be used throughout the study. At the same time, it is not recommended to inject the study drug into areas where skin shows signs of a previous injection site reaction. It is advised to change the injection site if any previous injection site reaction remains unresolved.

6.1.4. Leronlimab (PRO 140) - Post Injection Monitoring

Subject will be observed at approximately 30 minutes post-injection or longer if necessary, for injection site reaction as per CTCAE v5.0.

6.1.5. Leronlimab (PRO 140) – Toxicity Management

CONFIDENTIAL Page 58 of 101

Refer to Table 6-3 and Table 6-4 below. Recovery to acceptable levels must occur to allow leronlimab (PRO 140) continuation.

Table 6-3: Leronlimab (PRO 140) - Management for Injection Site Reactions

CTCAE Grade	Treatment Management
Grade 1 Mild	No dose adjustment is required.
Grade 2 Moderate	First Occurrence: No dose adjustment is required. Second Occurrence of the same event: Closely follow-up for resolution of the AE to Grade ≤ 1
Grade 3 Severe	Withhold treatment until symptoms resolve to: • Grade 1 or less
Grade 4 Life Threatening	Study treatment will be permanently discontinued

Table 6-4: Leronlimab (PRO 140) - Management for all Other Potential Toxicities (Attributable to Leronlimab)

CTCAE Grade (attributable to leronlimab)	Treatment Management
Grade 1 Mild	No dose adjustment is required.
Grade 2 Moderate	Withhold treatment until symptoms resolve to: • Grade 1 or less or baseline;
Grade 3 Severe	Study treatment will be permanently discontinued
Grade 4 Life Threatening	Study treatment will be permanently discontinued

6.1.6. Leronlimab (PRO 140) - Disposition

[figure not shown]
All drug supplies are to be used only for this protocol and not for any other purpose. The investigator must not destroy any drug labels or any partially used or unused drug supply until instructed by the Sponsor. At the conclusion of the study and as appropriate during the course of the study, the investigator will return all used and unused drug containers and drug labels to the drug distributor as directed by the Sponsor. A copy of the completed drug disposition form will be sent to CytoDyn, Inc. or to its designee.

6.1.7. Leronlimab (PRO 140) - Accountability

Study drug must be used in accordance with this protocol and only under the direction of the responsible investigator. The investigational site must maintain complete and accurate records showing receipt and disposition of all study drug, including master records listing the date of receipt, the number and nature of medication units received, and a dispensing record which includes each quantity dispensed, identification of the staff member/subject to whom dispensed, the date of

CONFIDENTIAL Page 59 of 101

dispensing, the intended study participant, and the identification of the preparer. All used and unused study kits will be retained by the investigational site until drug accountability can be confirmed by study CRA during the monitoring visits. Instructions will be provided by Sponsor regarding final disposition of all study drugs in compliance with applicable regulations.

CONFIDENTIAL Page 60 of 101

7. DESCRIPTION OF PROTOCOL ASSESSMENTS AND PROCEDURES

7.1. INFORMED CONSENT

A written informed consent will be obtained for this study by the Investigator or designee from all subjects prior to performance of any protocol-specific procedure. This study will be conducted in accordance with the provisions of the Declaration of Helsinki.

The Investigator must comply with applicable regulatory requirements and must adhere to the Good Clinical Practice (GCP) in the process of obtaining and documenting the informed consent. The Investigator, or designee, must also inform subjects of all pertinent aspects of the study. Before written informed consent is obtained from the subject, the Investigator or a person designated by the Investigator, must provide the subject enough time and opportunity to inquire about the details of the study and to decide whether or not to participate in the trial. All questions addressed by the subject about the study must be answered to the satisfaction of the subject. Prior to the subject's participation in the trial, the written informed consent must be signed and personally dated by the subject and by the person who conducted the informed consent discussion. Authorization for release of protected health information must also be obtained, as per local policies.

7.2. ASSESSMENT OF ELIGIBILITY

The Investigator must assess subject's continued eligibility for the study as per the Inclusion and Exclusion criteria, during the Screening Phase. The eligibility criteria are described in Section 3.3.1 (Inclusion Criteria) and Section 3.3.2 (Exclusion Criteria). In the event that the subject is not suitable or eligible for the study, the subject will be considered "screen failure".

7.2.1. Re-screening

If a subject fails initially to meet the eligibility criteria, and is later reconsidered for participation, the subject will be re-consented and assigned a new screening number at the time of re-screening. Subjects who fail their first screening attempt may be re-screened a maximum of once and may be enrolled in the study only if they meet all Inclusion and no Exclusion criteria when re-screened.

7.3. DEMOGRAPHIC INFORMATION

In this study the demographic information will include:

- Dates of ICF signature
- Date of birth
- Gender
- Race (American Indian or Alaska Native, Asian, Black or African American, Native Hawaiian or Other Pacific Islander, White, Not Reported, or Unknown)

CONFIDENTIAL Page 61 of 101

• Ethnicity (Hispanic or Latino, Not Hispanic or Latino, Not Reported, or Unknown)

• Use of tobacco products

7.4. MEDICAL HISTORY

A medical history will be recorded during the Screening Phase and will include:

- All ongoing medical conditions
- All previously resolved medical conditions that are relevant in the judgment of the Investigator
- Any prior medical conditions that have resolved within the last year

Events that emerge prior to the first treatment will be recorded in the medical history and not as AEs. Aside from being used to determine subject eligibility, this information will permit the Investigator to record the nature, duration and severity of any ongoing baseline medical conditions prior to the subject's receiving investigational product treatment.

Medical histories will be recorded using the body system categories outlined below:

- HEENT
- Cardiovascular
- Endocrinal
- Respiratory
- Gastrointestinal
- Substance Abuse
- Neurologic
- Genitourinary

- Lymphatic
- Musculoskeletal and Extremities
- Hematological
- Immunological
- Dermatologic
- Psychiatric-Psychological
- Other

For each relevant history, the following will be documented:

- Disease/disorder/condition
- Date of diagnosis
- History status (resolved or ongoing).

Note: For COVID-19 diagnosis, the number of days between the onset of symptoms and the initiation of treatment for each subject will be documented.

7.5. PHYSICAL EXAMINATION

The physical examination will include routine examinations for the following:

• Constitutional/General Appearance

CONFIDENTIAL Page 62 of 101

- Head, Ears, Eyes, Nose, Throat (HEENT)
- Neurologic
- Cardiovascular
- Musculoskeletal and Extremities
- Dermatologic
- Respiratory
- Gastrointestinal
- Genitourinary
- Lymphatic
- Psychiatric

Each abnormality will be recorded and the Investigator will record an assessment of its clinical significance.

7.6. VITAL SIGNS, HEIGHT AND WEIGHT

The following will be collected:

- Systolic Blood Pressure
- Diastolic Blood Pressure
- Heart Rate
- Temperature
- Respiratory Rate
- Height (only at V1)
- Weight

Note: Body Mass Index (BMI) will be auto-calculated using height and weight information in the EDC.

7.7. CONCOMITANT MEDICATIONS

All medications and therapies administered or taken by the subject beginning 30 days prior to Screening Visit and throughout the study will be recorded in the source documents and on the appropriate page of the Case Report Form (CRF). Additionally, all other investigational and off-label therapies for COVID-19 will be recorded. Subjects must be questioned at each study visit concerning any new medications or changes in current medications including over-the-counter medication and topical medication.

For each medication and non-study treatment, the following will be documented:

- Medication/treatment name (generic name may be used if trade name is unknown)
- Dose, unit, and frequency of dosing (individual dosages, not total daily dose).

CONFIDENTIAL Page 63 of 101

• Note: Each new dose of medication should be recorded as a separate entry, with the exception of medications that are given on a sliding scale. For these, it is acceptable to enter the range of the dosage, including the start and stop dates for which the specified dosage range was used.

- Route of dosing
- Indication for use
- The start date
- The stop date (if medication/therapy is not ongoing).

7.7.1. Excluded Medications

The following medications are prohibited while on study drug:

- Hydroxychloroquine, oral or parenteral corticosteroids, immunosuppressants, or immunomodulating agents
- Albuterol as nebulizer for treatment of COVID-19
- Other CCR5 antagonists
- Other investigational products

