3.3.2. Exclusion Criteria

Potential subjects meeting any of the following criteria will be excluded from enrollment:

- 1. Exhibiting signs of moderate or severe pulmonary disease (such as COPD, asthma, or pulmonary fibrosis)
- 2. Ongoing requirement of oxygen therapy
- 3. Pulse oxygen saturation (SpO2) of <94% on room air at the time of screening
- 4. History of splenectomy
- 5. Liver cirrhosis or patient showing signs of clinical jaundice at the time of screening
- 6. Chronic kidney disease stage 4 or requiring dialysis at the time of screening

CONFIDENTIAL Page 42 of 101

- 7. NYHA Class III or IV congestive heart failure (CHF)
- 8. Exhibiting signs of uncontrolled hypo-or hyper- thyroidism at the time of Screening
- 9. Uncontrolled rheumatologic disorders at the time of screening
- 10. History of organ transplantation or are candidates for organ transplantation at the time of screening
- 11. History of Chronic Fatigue Syndrome prior to COVID19 infection
- 12. History of fibromyalgia prior to COVID-19 infection
- 13. History of major psychiatric disorder including bipolar disorders, schizophrenia, schizoaffective disorder, major depression. Patients with major depression can be enrolled if patient has had no episode within the past year or is considered in remission or controlled by treatment.
- 14. Any malignancy within the past 5 years, excluding successfully treated basal cell carcinoma or squamous cell carcinoma without evidence of metastases.
- 15. Any other clinically significant serious systemic diseases which would interfere with study conduct or study results interpretation per the Investigator.
- 16. Treatment with immunosuppressive or immunomodulatory medications within 5 half-lives prior to screening. Patients on replacement therapy for adrenal insufficiency will be allowed. Patients on stable (> 3 months) low dose corticosteroid ≤ 5 mg Prednisone will be allowed.
- 17. History of allergic reactions attributed to compounds of similar chemical or biologic composition to leronlimab (PRO 140) are not eligible
- 18. Ongoing use of CCR5 antagonist
- 19. Inability to provide informed consent or to comply with test requirements
- 20. Consideration by the investigator, for safety reasons, that the subject is an unsuitable candidate to receive study treatment
- 21. Pregnancy or breast feeding
- 22. Participating in another study for an investigational treatment

CONFIDENTIAL Page 43 of 101

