11.4.1. Major Protocol Deviation or Violation

A major protocol deviation or violation is a deviation from the IRB approved protocol that may affect the subject's rights, safety, or well being and/or the completeness, accuracy and reliability of the study data. Examples of this include:

- Failure to obtain informed consent prior to initiation of study-related procedures
- A research subject does not meet the protocol's eligibility criteria but was enrolled without prior approval from the sponsor.
- A research subject received the wrong treatment or incorrect dose.
- A research subject met withdrawal criteria during the study but was not withdrawn.
- A research subject received a prohibited concomitant medication.
- Failure to treat research subjects per protocol procedures that specifically relate to primary efficacy outcomes.
- Changing the protocol without prior sponsor and IRB approval.
- Multiple minor violations of the same nature after multiple warnings.

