8.1.2 Protocol Deviations

Protocol deviations will be identified and classified as minor or major before un-blinding.

Protocol deviations for all randomized subjects will be listed as by-subject listing and major deviations will be summarized descriptively according to the following categories:

- Did not meet Inclusion/Exclusion criteria but entered into study
- Developed withdrawal criteria during the study but not withdrawn
- Received excluded concomitant medication
- Study treatment dosing deviation

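### Exclusion 16 admits patients on adrenal replacement or stable prednisone of 5 mg or less, but protocol 7.7.1 bars oral and parenteral corticosteroids on treatment without exception

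*Combined protocol and SAP*

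**What the plan says.** Two rules govern corticosteroids.

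**At entry.** Exclusion 16 (protocol synopsis and 3.3.2, same wording) bars "Treatment with immunosuppressive or immunomodulatory medications within 5 half-lives prior to screening". It then makes two allowances: "Patients on replacement therapy for adrenal insufficiency will be allowed", and "Patients on stable (> 3 months) low dose corticosteroid ≤ 5 mg Prednisone will be allowed".

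**On treatment.** Protocol 7.7.1 opens with "The following medications are prohibited while on study drug", and its first bullet is "Hydroxychloroquine, oral or parenteral corticosteroids, immunosuppressants, or immunomodulating agents". It does not refer back to exclusion 16. Section 7.7.2, on allowable medications, names only empirical antibiotics for secondary bacterial infection.

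**Consequences of breaking the on-treatment rule.** Protocol 11.4.1 includes in its examples of major deviations "A research subject received a prohibited concomitant medication". SAP 8.1.2 has "Received excluded concomitant medication" as one of four categories for summarising major deviations, and also states: "Protocol deviations will be identified and classified as minor or major before un-blinding". The per-protocol set (protocol 8.9.1.2, SAP 6.2) leaves out subjects with major violations and is supportive for the primary and secondary efficacy endpoints. The mITT set (protocol 8.9.1.1, SAP 6.1) takes every subject who received at least one dose and is the primary efficacy set.

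**The concern.** A patient can satisfy the entry criteria because of an allowance and be in breach of the medication rules from the first dose by continuing the same drug. Each course open to the site has a cost.

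- **Stop the steroid.** Withdrawing adrenal replacement puts the patient at risk. Stopping a stable low dose at the time of randomisation also changes background treatment just as the symptom diary begins.
- **Decline the patient.** Inclusion 8 requires a subject to be able to comply with study restrictions. A site that takes 7.7.1 at its word could turn away someone exclusion 16 admits, and the allowance would then have no effect.
- **Enrol and continue.** The site records a prohibited medication for use that the protocol allowed at entry, and the subject's place in the per-protocol set depends on a later rating.

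Sites may choose differently, since nothing tells them which rule prevails.

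**Working it through.** The plan gives no figure to reproduce here, so the check is a comparison of the texts.

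**Step 1. Do the two rules cover the same drugs?** For corticosteroids, yes. Both allowances in exclusion 16 concern corticosteroid treatment, and 7.7.1 covers corticosteroids given by mouth or by injection. For other immunosuppressants and immunomodulators, exclusion 16 gives no allowance, so the two sections agree there. Inhaled, intranasal and topical steroids fall outside the wording of 7.7.1. The conflict is therefore limited to oral or parenteral corticosteroids used under one of the two allowances.

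**Step 2. Do they cover different periods, so that both can hold?** The main clause of exclusion 16 looks back from screening, but its allowances are in the present tense and describe people who are on the therapy. Replacement treatment and a dose held stable for more than three months are continuing treatments. The rule in 7.7.1 runs for the whole time on study drug and is not worded as a ban on new starts. With screening at most 7 days before the first dose, a patient on continuing therapy passes directly from one rule to the other.

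**Step 3. Is there a reconciling text elsewhere?** Section 7.7.2 supplies none. Section 7.7 requires sites to record medications and ask about changes, but exempts nothing. The SAP contains no exception. The immediate-hazard provision in 11.3 allows a protocol change before IRB approval; it does not alter what 7.7.1 says.

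**Step 4. What follows for the analysis sets?**

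| Set | Rule | Effect of continuing a permitted steroid |
|---|---|---|
| mITT (primary) | At least one dose | None; the subject stays |
| Per protocol (supportive) | mITT with no major violation | Removed if the use is rated major; kept if rated minor |

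**Step 5. Scale.** The documents plan 50 randomised subjects at 1:1 and give no number on permitted steroids. Assume that all 50 are dosed and the arms are equal at 50 / 2 = 25. Each subject whose use is rated major then accounts for 1 / 50 = 2% of the dosed subjects, or 1 / 25 = 4% of one arm, in the per-protocol set. The mITT loss is 0. These are per-subject figures, not a forecast, because the count may be zero.

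**The case against.** The best defence is that the intent is plain. Exclusion 16 is the more specific provision, and admitting these patients only to forbid their treatment on Day 0 would make no sense. A sensible investigator would read 7.7.1 as aimed at new steroids, and nothing in the plan directs anyone to taper or withdraw existing therapy. The examples in 11.4.1 illustrate deviations that may affect safety or data reliability, and use that was allowed at entry is a natural candidate for a minor rating under SAP 8.1.2. The investigator may also exclude a patient for safety reasons under exclusion 20. The trial is exploratory, has no power calculation, and uses the per-protocol set only as support.

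Most of this stands as a limit on the consequences. It does not remove the contradiction. The sensible reading is not the written one, and protocol 11.4 obliges investigators to follow the requirements as written. If sites rely on intent, they may resolve the conflict in different ways.

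Three stronger readings are tempting, and the documents do not support them.

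- A reader might infer that these subjects will be dropped from the per-protocol set. The minor-or-major classification before unblinding leaves that open.
- A reader might infer that the primary analysis set is compromised. The mITT definition depends only on dosing.
- A reader might infer that the whole first bullet of 7.7.1 conflicts with eligibility. Only its corticosteroid part does.

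**Conclusion.** The point holds as an internal inconsistency confined to corticosteroids: a rule that gives the wrong result if followed as written, not merely a missing detail. Confidence in the mismatch is high, because both texts are explicit and no other section bridges them. The consequences are conditional. They require that at least one patient is enrolled, or considered, under an exclusion 16 allowance. The safety consequence also requires a site to follow 7.7.1 literally and stop the therapy. The per-protocol consequence requires the steroid to be continued and its use rated major.

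The correction should be made. The potential harm in stopping adrenal replacement justifies it even if few or no patients are affected.

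**What to change.** Amend the first bullet of protocol 7.7.1 by inserting, directly after the word corticosteroids:

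*(except replacement therapy for adrenal insufficiency and stable low-dose corticosteroid ≤ 5 mg prednisone, as permitted by exclusion criterion 16, which may continue and are not prohibited medications)*

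Leave the rest of the bullet as it is. In particular, keep the limit to oral or parenteral routes. Dropping it would newly ban inhaled, intranasal and topical steroids, which 7.7.1 does not prohibit, and would create deviations of its own. The ban on other immunosuppressants and immunomodulators needs no exception.

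The cost is one clause in a protocol amendment, with the sponsor's agreement and the IRB approval that 11.3 requires. No SAP change is needed: once the permitted use is no longer prohibited, it no longer falls into the excluded-medication category of SAP 8.1.2.
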